5 HYPOTHESES

No hypotheses will be tested due to the brief CSR.

6 DEFINITIONS

Baseline

In general, the baseline value will be considered the last measurement observed prior to taking the first dose of study treatment. For ECG, if a set of triplet ECG are the last ECG collected prior to taking the first dose of study treatment, the average of the triplet ECG will be considered as baseline.

For subjects who are randomized and never receive study treatment, the baseline value will be the last assessment before randomization (on the day of or before randomization).

Investigational Product/Study Treatment

‘Investigational product’ or ‘study treatment’ is used to reference only infigratinib or placebo.

Long-term Follow-up Phase

The long-term follow-up phase begins after the safety follow-up visit and continues until death or full consent withdrawal. Efficacy assessments including radiographic assessments, cystoscopy and urine cytology will continue to be performed until recurrence by BICR (local/regional invasive or metastatic) or metastatic recurrence by investigator assessment, whichever comes later. Subjects who develop recurrence by BICR (local/regional invasive or metastatic) or metastatic recurrence by investigator assessment prior to the long-term follow-up phase will not be followed for disease status during the long-term follow-up phase. After that time, subjects will be followed for survival every 6 months for 1 year, then annually thereafter (via telephone or office visit) for 1 year after the time when the final DFS event goal is reached (ie, EOS).

Overall Survival Time (OS)

Overall survival time is calculated as the number of months from randomization to death (date of death - date of randomization + 1)/(365.25/12). Subjects who have not died (no record of death) or are lost to follow up will be censored at the date of last known to be alive. Subjects who

withdraw consent for study participation, including consent to be followed, will be censored on the date of withdrawal.

Metastasis-free Survival Time (MFS)

The investigator reviewed MFS is defined as the time from randomization to any metastatic recurrence as determined by the investigator or death due to any cause, whichever occurs earlier. Subjects without documented metastatic recurrence and are still alive, will be censored at the last radiology assessment, or at the time of randomization if no radiology disease assessments are performed after the baseline visit.

Disease-free Survival Time (DFS)

Disease-free survival time is calculated as the number of months from randomization to the date of local/regional invasive or metastatic recurrence or death due to any cause (referred as DFS event) ((date of DFS event - date of randomization + 1)/ (365.25/12)). Subjects without recurrence (local/regional invasive or metastatic) or death will be censored at the last radiology assessment if previous cystoscopy result within 6 months is negative for muscle invasive disease, otherwise, DFS will be censored at the last complete recurrence assessment. Subjects who have no disease assessments after baseline will be censored on the randomization date. The primary DFS endpoint will be based on the central review (BICR), while for the secondary endpoint, the investigator reviewed DFS will be based on investigator review.

DFS including intraluminal low risk recurrence

The investigator reviewed DFS including intraluminal low risk recurrence is defined as the time from randomization to any recurrence as determined by investigator, or death due to any cause, whichever occurs earlier. For subjects without documented recurrence and are still alive, they will be censored at the last complete disease assessment (or, if no disease assessments are performed after the baseline visit or no death has been recorded, at the time of randomization).

Relative dose intensity

The relative dose intensity is defined as cumulative actual dose a subject have received divided by the planned cumulative dose. For example, a subject takes study drug from Day 1 to Day 21 at 125 mg/day; then from Day 29 to Day 30 at 100 mg/day, and end treatment afterward. The cumulative actual dose $=(21*125)+(100*2)=2825$ mg; the planned cumulative dose $=(21*125)+(125*2)=2875$ mg. The relative dose intensity $= 2825/2875=98.3\%$.

Study Day 1

Study Day 1 is defined as the day of the first administration of study treatment after randomization.

Treatment Duration

Treatment duration is defined as last dose date – first dose date +1.

On Treatment Period

On treatment period is defined as first administration of study treatment through 30 days after the last administration of study treatment inclusively.

Treatment-emergent Adverse Event

A treatment-emergent adverse event is defined as an adverse event that occurs on or after the first administration of study treatment and within 30 days after the last administration of study treatment.

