8.1.2 Discontinuation from Study

Subjects have the right to withdraw from the study at any time without prejudice. Pending the criteria for which the subject withdraws consent, as listed below, those specified assessments must be discontinued and no further assessments conducted. Further attempts to contact the subject are not allowed unless safety findings require communication or follow-up.

Subjects may be discontinued from the study for the following reasons:

- Subject's formal withdrawal of informed consent. If a subject withdraws consent from study participation, the level of withdrawal must be documented. Below are the possible levels of subject's withdrawals:
 - Full withdrawal: withdrawal from all study treatments, procedures, assessments, and any type of follow-up (survival, new anticancer therapy, etc.)
 - Withdrawal from all study assessments or procedures; survival follow-up is permitted, together with collection of data related to initiation of new anticancer therapy.
 - Withdrawal from survival follow-up (subject or family cannot be contacted; public record data can be reviewed).
 - If a subject withdraws from the study, the subject may request destruction of any samples taken and not tested, and the investigator must document this in the study records and notify the sponsor immediately.
- Investigator request.
- Lost to follow-up (defined as no contact after 3 documented attempts by telephone followed by 1 attempt via certified letter).
- Discontinuation of the study by the sponsor.

- Protocol deviation.
- Study complete.
- Death.
- Other.

The reason for discontinuation from the study is to be documented in the eCRF, including the exact level of subject's withdrawal from the study. The investigator should make every effort to determine why a subject is lost to follow-up or withdraws consent and record this information in the eCRF. Further, if a subject is withdrawn due to protocol violation or Investigator's request, specifics are to be recorded in the eCRF.

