9.9 Survival Follow-up and New Antineoplastic Therapies

After either BICR-confirmed metastatic recurrence, or investigator-confirmed metastatic recurrence if BICR-confirmed local/regional or contralateral recurrence has already occurred, subjects will be followed up for survival status every 6 months for 1 year, then annually thereafter (via telephone or office visit) for 1 year (± 14 days) after the final DFS event goal is reached (ie, EOS).

Antineoplastic therapies since discontinuation of study treatment should also be collected for 1 year (± 14 days) after the final DFS event goal is reached (ie, EOS). Use of anticancer therapy will be collected for all subjects, including from the time of study treatment discontinuation, regardless of reason for discontinuation. For subjects started on a non-study related anticancer therapy after discontinuing from study treatment, imaging assessment of disease status should continue until metastatic recurrence by BICR or metastatic recurrence by investigator assessment if local/regional or contralateral invasive recurrence by BICR has already occurred.

If a subject requests withdrawal of consent specifically from survival follow-up, this request must be documented in the subject's medical record. In such cases, the site staff may use public information source (such as county records) to obtain information about survival status and only as appropriate per local regulations.

After the EOS (1 year after the DFS primary analysis), subjects will continue to be followed for OS (under a separate protocol) for approximately 14 years, or all of the subjects die or drop from this follow up, whichever is earlier, referred to as long-term OS follow up. The data for the long-term OS will be reported in a separate study report.

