11.3.3 Efficacy Analyses

The primary objective of the study is to compare the centrally reviewed DFS of subjects with invasive urothelial cancer with susceptible FGFR3 alterations treated with infigratinib vs placebo following nephroureterectomy, distal ureterectomy, or cystectomy.

The primary endpoint is centrally reviewed DFS, from date of randomization to local/regional or contralateral invasive or metastatic recurrence (according to central review) or death due to any

cause, whichever occurs earlier. Criteria for recurrence are specified in Section 10.1. For subjects without a bladder who are alive and without recurrence (local/regional or contralateral invasive or metastatic) by BICR, DFS will be censored at the last radiology assessment. For subjects with a bladder who are alive and without recurrence, DFS will be censored at the last radiology assessment if the previous cystoscopy result within 6 months is negative for muscle invasive disease, otherwise DFS will be censored at the last complete recurrence assessment. Subjects who have no disease assessments after baseline or no death recorded will be censored on the randomization date.

Investigator-reviewed DFS including intraluminal low-risk (noninvasive, low-grade, or high-grade) recurrence is defined as the time from randomization to any recurrence as determined by the investigator, or death due to any cause, whichever occurs earlier. For subjects without documented recurrence and who are still alive, they will be censored at the last complete disease assessment (or, if no complete disease assessments are performed after the baseline visit or no death recorded, at the time of randomization day).

Investigator-reviewed MFS is defined as the time from randomization to any metastatic recurrence as determined by the investigator or death due to any cause, whichever occurs earlier. For subjects without documented metastatic recurrence and who are still alive, they will be censored at the last radiology assessment (or, if no radiology assessments are performed after the baseline visit or no death recorded, at the time of randomization day).

OS is defined as date of randomization to death. For subjects without documented death, they will be censored at the last known to be alive date.

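### Does the SAP's overall-survival withdrawal rule discard deaths that are found in public records?

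*SAP*

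**What the plan says.** Protocol section 11.3.3 has one censoring rule for OS: "For subjects without documented death, they will be censored at the last known to be alive date". It has no separate rule for withdrawal.

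SAP section 6 (Overall Survival Time) has two censoring sentences. The first censors subjects with no recorded death, or lost to follow-up, at the date last known alive. The second covers subjects who "withdraw consent for study participation, including consent to be followed, will be censored on the date of withdrawal"; it does not restate the condition about death.

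Protocol section 8.1.2 requires that "If a subject withdraws consent from study participation, the level of withdrawal must be documented" and that the eCRF hold the reason for leaving, "including the exact level of subject's withdrawal from the study". It lists three levels:

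- "Full withdrawal: withdrawal from all study treatments, procedures, assessments, and any type of follow-up (survival, new anticancer therapy, etc".)
- Stopping assessments and procedures while survival follow-up continues.
- "Withdrawal from survival follow-up (subject or family cannot be contacted; public record data can be reviewed".)

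Protocol section 9.9 takes up the third level: "If a subject requests withdrawal of consent specifically from survival follow-up, this request must be documented in the subject's medical record". Sites may then use public sources "to obtain information about survival status and only as appropriate per local regulations".

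In SAP section 6, DFS is censored only when there is neither recurrence nor death, and MFS only in subjects who are alive without metastatic recurrence. Neither has a withdrawal-date rule. SAP section 8.10.1 lists all deaths in treated subjects.

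**The concern.** Read literally and in isolation, the SAP sentence censors a withdrawn subject at the withdrawal date even if a death is later documented. The protocol foresees such documentation for subjects who leave survival follow-up, because public records stay open to review. That level sits in section 8.1.2 under withdrawal of consent from study participation, and the SAP sentence uses similar words, so a programmer could apply the rule to it.

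The same death would then be an event in DFS and MFS (if no recurrence came first) and a censored observation in OS. That subject's OS time would be shorter than the DFS time, the OS curve would sit too high after the death, and it would disagree with the death listing. It would also depart from the OS rule in protocol section 11.3.3.

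**Working it through.** **Step 1. Apply the SAP sentence to each level in protocol 8.1.2** (subject with no earlier recurrence).

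| Level | Does the SAP sentence apply? | Can a later death be recorded? | Conflict between OS and DFS/MFS |
|---|---|---|---|
| Full withdrawal | Yes | Normally not; no records route is given | Little or none |
| Assessments only | No; consent to be followed remains | Yes | None; death counts in all three |
| Survival follow-up only | Only on the wider reading | Yes, from public records where local rules allow | Yes, on that reading |

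**Step 2. Which reading fits the text?** The SAP sentence needs both elements: consent to participate is withdrawn, and that withdrawal extends to being followed. This matches the full-withdrawal level, which covers every type of follow-up. Protocol 9.9 treats leaving survival follow-up as a separate, specific request. In the same SAP section, the long-term follow-up phase ends at death or when consent is fully withdrawn. All three point to the narrower reading.

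**Step 3. One subject on the wider reading.** Assumed dates: withdrawal on day 300 after randomization, death from public records on day 480, no recurrence. The SAP formula is (date − randomization date + 1)/(365.25/12), and 365.25/12 = 30.4375.

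- OS: censored at 301/30.4375 = 9.9 months.
- DFS and MFS: events at 481/30.4375 = 15.8 months.

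**Step 4. Effect on the OS curve on the wider reading.** Let S be the Kaplan-Meier estimate at withdrawal, n the number at risk in the arm (this subject included), and k the other deaths between the two dates, with no other censoring. Just after the omitted death:

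- Subject censored at withdrawal: S(n−1−k)/(n−1).
- Death counted: S(n−1−k)/n.
- Difference: S(n−1−k)/(n(n−1)), which is S/n when k = 0 and smaller otherwise.

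The documents do not give the number randomized, so n and S (0.8 to 1.0) are assumed. Differences in percentage points:

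| n at risk | k = 0 | k = 2 |
|---|---|---|
| 10 | 8.0 to 10.0 | 6.2 to 7.8 |
| 20 | 4.0 to 5.0 | 3.6 to 4.5 |
| 40 | 2.0 to 2.5 | 1.9 to 2.4 |

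**Step 5. Is censoring at withdrawal itself biased?** A simulation of 200,000 subjects used assumed, independent yearly hazards (death 0.08 or 0.12; withdrawal 0.025 or 0.10) and assumed follow-up of 0.5 to 2.5 or 3 to 5 years. True 2-year OS is exp(−0.16) = 85.2% or exp(−0.24) = 78.7%.

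- Censoring at withdrawal gave 85.1 to 85.3% and 78.6 to 78.8%.
- Adding later deaths without also updating the dates last known alive lowered 2-year OS by 0.2 to 1.9 points.
- Updating both gave 85.1 to 85.3% and 78.6 to 78.8% again.

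So the withdrawal-date rule is sound when withdrawal is unrelated to prognosis, and picking up deaths alone can do harm.

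**The case for a change.** The strongest case for a change is that it is cheap and removes all doubt. The withdrawal level is already in the eCRF, a few added words would settle the rule, and OS, DFS, MFS and the death listing would then agree on either reading. OS remains a reported secondary endpoint, and with few subjects randomized a single death can be visible on a curve. The wider reading is not absurd either, since section 8.1.2 places the survival-follow-up level under withdrawal from study participation.

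The textual part stands: the condition is missing from that sentence and no level is named. What does not stand is the step from there to a flaw in the analysis. The SAP presents itself as detailing the analyses outlined in the protocol, and the protocol censors only subjects without a documented death. Read together, the SAP sentence sets a censoring date for withdrawn subjects; it does not instruct anyone to set aside a known death. Protocol section 11.1 also leaves the details of missing-data handling to the SAP, so a withdrawal-date rule is arguably such a detail. And on the natural reading, the added words would only write down what is already meant.

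**Conclusion.** No change follows. This is loose wording that an analyst with the protocol at hand would fill sensibly: censor at withdrawal those who withdraw fully and have no recorded death, and count documented deaths.

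The effect is little or none on the natural reading. For any effect, a subject must leave survival follow-up specifically, die afterwards, be found in public records where that is allowed, and be programmed under the wider reading. The documents give no count of such subjects, and it may be zero. The shifts in Step 4 are per omitted death and depend on assumed numbers at risk.

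No decision rests on the result. SAP sections 5 and 8.1 state that no hypotheses are tested and that time-to-event endpoints are summarised by Kaplan-Meier only, in an abbreviated report of a study closed early for business reasons. A mismatch in a treated subject would show when the OS data are set against the death listing. The finding that withdrawal-date censoring is unbiased assumes that withdrawal is independent of prognosis, which the documents neither support nor contradict.

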7 ANALYSIS POPULATION

The primary analyses for the efficacy endpoints will employ the intent to treat (ITT) population. Safety analyses will be performed on the safety analysis population.

7.1 Intent to Treatment Population

The intent to treatment population includes all subjects who are randomized. Subjects will be analyzed by the treatment group randomized to, regardless of the treatment received. This intent to treatment analysis set will be the primary analysis set for efficacy.

7.2 Safety Population

The safety population includes all subjects who are randomized and receive at least 1 administration of infigratinib or placebo. Subjects will be analyzed by the treatment received.

7.3 Subgroup Analyses

The summaries of adverse events may be performed for subgroups, as appropriate, defined by

- Sex (male vs female)
- Age at study enrollment (< 65 years vs \geq 65 years)
- Race

8 STATISTICAL METHODS OF ANALYSIS

8.1 General Principles

With the limited number of patients randomized at the time of the decision to early terminate the study, the number of disease-free survival events required to assess the efficacy objectives was not achieved to the futility of the study. No formal inferential testing of efficacy will be done. In general, any values, such as those due to unit conversion, will be reported rounding to the same number of decimal places as the original data. Month or year converted from day will be reported rounding to one place after the decimal point.

In general, categorical variables will be summarized using counts and percent. Percent will be displayed to one place after the decimal point, with the exception of 100%, which will be displayed without additional decimal places.

Continuous variables will be summarized using number of subjects, mean, median, standard deviation, Q1, Q3, minimum, and maximum.

Time to event endpoints will be analyzed by Kaplan Meier (K-M) method. No statistical test will be conducted.

SAS statistical software, version 9.4 or later, will be used for all analyses.

If departures from these general conventions are present in the specific evaluations section of this SAP, those conventions will take precedence over these general conventions.

8.2 Handling of Missing Data

Partial dates will be defined as dates that are missing certain elements of the date field. This may include missing information for the month, day, or year, or two of these elements, but not all three.

Partial dates for adverse events where the start day is missing will be imputed as the first day of the month unless the start month of the adverse event is the same as the month when the treatment is initiated. In this case, the start day will be imputed as first dose date. The adverse event will be counted as treatment emergent adverse event. If the month, year, both month and year, or the entire start date is missing, then no data imputation will be implemented. However, these events will be counted with regard to treatment adverse event as long as there is no clear evidence to indicate adverse event starts before first dose date or after last dose date +30 days.

In general, for all other partial missing dates, if day is missing, day 15 will be imputed. No other imputation will be done if month or year is missing.

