10.5.1.3 Recording Adverse Events

After a subject signs the molecular prescreening ICF and/or the main study ICF and until a subject is randomly assigned to study treatment, AEs will only be captured if they meet the definition of serious and are reported to be causally related with study procedures (eg, an invasive procedure such as biopsy). Any other appearance of (or worsening of any pre-existing) undesirable sign(s), symptom(s), or medical condition(s) should be recorded as medical history.

Before randomization, any SAEs reported as causally related with study procedures will be captured on a paper SAE Report form. After randomization, all AEs and all SAEs will be captured and reported in the eCRF.

Conditions already present at the time of informed consent should be recorded in the Medical History eCRF.

AEs (including lab abnormalities that constitute AEs) should be described using a diagnosis whenever possible, rather than individual underlying signs and symptoms. When a clear diagnosis cannot be identified, each sign or symptom should be reported as a separate AE.

The following information is to be captured in the eCRF for each AE: severity grade (CTCAE version 5.0, Grade 1-5); duration (start and end date); relationship to study drug; action taken with respect to study drug; whether medication or therapy was given; outcome; and whether the event was serious and seriousness criteria.

AE monitoring should be done from the time of informed consent and continue through 30 days after the last dose of study drug.

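### SAP 8.2 dates an AE with a missing start day to first dose and counts it as treatment-emergent even when its recorded end date falls before dosing

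*SAP*

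**What the plan says.** SAP 8.2 (Handling of Missing Data) treats incomplete AE start dates in two branches.

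- **Only the day missing.** The default is "Partial dates for adverse events where the start day is missing will be imputed as the first day of the month". The exception is a start month equal to the month in which treatment began: "In this case, the start day will be imputed as first dose date". The next sentence fixes the classification: "The adverse event will be counted as treatment emergent adverse event". Neither sentence carries a condition on the end date.
- **More than the day missing.** "If the month, year, both month and year, or the entire start date is missing, then no data imputation will be implemented". A safeguard follows: "these events will be counted with regard to treatment adverse event as long as there is no clear evidence" that they began before first dose or after the 30-day window.

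A last sentence in the same section sets the day to 15 for all other dates that lack only the day.

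SAP 6 defines a treatment-emergent event as "an adverse event that occurs on or after the first administration of study treatment" and within 30 days after the last administration. SAP 8.10.1 says the same in terms of when the event starts. Protocol 11.1 leaves missing-data handling to the SAP, so no protocol rule overrides this one.

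**The concern.** Imputing to first dose is a sensible conservative default when it is unknown whether an event began before or after dosing. A recorded end date before first dose removes that doubt. The rule still places the start after the end and sends the event to the treatment-emergent tables. The branch with more date information thus has less protection than the branch with less.

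What is at stake is the correctness of individual AE records and flags. The trial closed early and, under SAP 5 and 8.1, no hypothesis is tested. Descriptive safety tables are therefore a main output, and a known pre-dose event should not appear in them as an on-treatment one.

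**Working it through.** The plan states no figure to reproduce. The check is whether the rule, applied literally, can contradict the definition, and for which records.

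**Inputs**

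1. AE data in the eCRF begin at randomization. Protocol 10.5.1.3: "After randomization, all AEs and all SAEs will be captured and reported in the eCRF". Before that, only serious events related to study procedures are captured, on a paper form; other conditions go to medical history.
2. Treatment starts within 1 week of randomization (Protocol 7.3, 9.3 and Table 2 footnote r).
3. Start and end dates are both collected for each AE (Protocol 10.5.1.3).
4. The imputation rule and the definition are as set out above.

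**Does the safeguard cover the missing-day branch?** Its subject, in "these events will be counted with regard to treatment adverse event as long as there is no clear evidence", is the group named in the sentence just before it: events missing month, year or the whole date. The missing-day branch has already been closed by "The adverse event will be counted as treatment emergent adverse event". Even on a generous reading, the condition "as long as there is no clear evidence to indicate adverse event starts before first dose date" governs only whether the event is counted. It would not move the imputed start, which would still fall after the end.

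**Illustration (assumed dates).** Randomized 10 March, first dose 17 March, AE start recorded as March with no day, AE end recorded as 14 March.

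- Rule as written: start = 17 March; duration = 14 − 17 + 1 = −2 days; treatment-emergent = yes.
- Definition in SAP 6: the event was over on 14 March, before 17 March; treatment-emergent = no.

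**All cases in the gap.** With a gap of g days between randomization and first dose, all in one calendar month, the number of possible start/end day pairs lying wholly before first dose is g(g + 1)/2. Coding the rule and running every pair gives:

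| Gap (days) | Possible pairs | Misdated and misflagged |
|---|---|---|
| 0 | 0 | 0 |
| 1 | 1 | 1 |
| 3 | 6 | 6 |
| 7 | 28 | 28 |

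This is what logic requires: the imputed start equals first dose, and every such end date is earlier. The table shows that the rule has no exception. It does not show how often such records occur.

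**With an end-date condition.** In the illustration, the start becomes the later of 1 March and 10 March, that is 10 March, which is before the 14 March end, and the flag is no. An event that is ongoing, or that ends on 20 March, keeps start = 17 March and flag = yes.

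**Why the condition must use recorded dates only.** Take first dose 17 March, with both start and end recorded as March without a day. The day-15 rule, which on its face covers AE end dates, sets the end to 15 March, before first dose. A condition applied to that imputed date would remove the flag from an event that may well have begun on treatment.

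**The case against.** The strongest reply is that the case is too narrow to matter, and most of that stands. A false flag needs an event that starts and ends between randomization and first dose, starts in the calendar month of first dose, has no start day, and has a known pre-dose end date. With same-day dosing it cannot occur. Protocol 12.3 and 12.4 provide automatic checks and queries for discrepant and missing values, and Protocol 10.5.1.4 requires serious events to be reported within 24 hours of learning of them. A serious event with these gaps is therefore an unlikely survivor. None of the tables planned in SAP 8.10.1 uses AE duration, and the listing of all AEs with flags would let a reader spot a crossed date. The rule treats both arms alike and leans toward over-counting. The table shells are in a separate document, so handling at output level is not known.

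This limits the size of the point but does not remove it. Imputation rules exist for dates that stay incomplete after queries, and conservatism is a reason to over-count only where there is doubt.

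Two stronger readings are tempting, and the documents do not support either:

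- A reader might take 7/30 = 23% as the size of the problem. That is the largest share of a 30-day month that the gap can occupy. It is not a misclassification rate or a count of events.
- A reader might infer that one misclassified event would visibly shift an arm's percentage. The SAP says only that enrollment was limited and gives no arm size. If 20 to 50 treated subjects per arm are assumed, one subject moves an incidence by 1/50 = 2 to 1/20 = 5 percentage points. That holds only if such a record exists and the subject is not already counted in that row. Nothing in the documents shows that one does.

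**Conclusion.** The rule is wrong as written, at a low level of importance. For any AE with a missing start day in the first-dose month and a complete recorded end date before first dose, SAP 8.2 produces a start after the end and a treatment-emergent flag that SAP 6 and 8.10.1 exclude. The effect is expected to be rare, the number of affected events cannot be computed from the documents, and no efficacy result is affected.

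The conclusion rests on two readings: that the AE eCRF page opens at randomization, as Protocol 10.5.1.3 states, so exposure is confined to a gap of at most 1 week; and that the safeguard belongs only to the branch it follows. The default of imputing to first dose is not itself at fault; only the missing end-date condition is.

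**What to change.** Add to SAP 8.2, in the missing-day branch:

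- The first-dose-date imputation and the treatment-emergent flag apply unless a complete, recorded (not imputed) AE end date is before first dose.
- In that case, impute the first of the month, or the randomization date if later, and do not flag the event.
- AEs with a missing or partial end date, or an end on or after first dose, keep the present rule. An end date imputed to day 15 must not be used to remove a flag.

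When both days are missing, the imputed start and the day-15 end can still cross. That is a conflict between two imputations, not evidence about the event, and the flag should stay.

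The cost is one sentence and one programming condition on a date already collected. A query for AEs with a missing start day in the first-dose month and a recorded end before first dose would show at once whether any record is affected.
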